8.2.4.1. Hepatic Safety Monitoring

8.2.4.1.1. Close Hepatic Monitoring

Laboratory tests (Appendix 3 [Section 10.3]), including ALT, AST, ALP, TBL, direct bilirubin, GGT, and creatine kinase, should be repeated within 48 to 72 hours to confirm the abnormality and to determine if it is increasing or decreasing, if 1 or more of these conditions occur:

If a participant with baseline results of	develops the following elevations:		
ALT or AST <1.5× ULN	ALT or AST ≥3× ULN		
ALP <1.5× ULN	ALP ≥2× ULN		
TBL <1.5× ULN	TBL ≥2× ULN (except for participants with Gilbert's syndrome)		
ALT or AST ≥1.5× ULN	ALT or AST ≥2× baseline		
ALP ≥1.5× ULN	ALP ≥2× baseline		
TBL ≥1.5× ULN	TBL ≥2× baseline (except for participants with Gilbert's syndrome)		

Abbreviations: ALP = alkaline phosphatase; ALT = alanine aminotransferase; AST = aspartate aminotransferase; TBL = total bilirubin; ULN = upper limit of normal.

If the abnormality persists or worsens, clinical and laboratory monitoring, and evaluation for possible causes of abnormal liver tests should be initiated by the investigator in consultation with the Lilly-designated medical monitor. At a minimum, this evaluation should include

- physical examination and a thorough medical history, including
 - o symptoms, and
 - o recent illnesses, for example, heart failure, systemic infection, hypotension, or seizures
- recent travel
- history of concomitant medications including
 - o over-the-counter, and
 - o herbal and dietary supplements
- history of alcohol drinking, and
- other substance abuse.

Initially, monitoring of symptoms and hepatic biochemical tests should be done at a frequency of 1 to 3 times weekly, based on the participant's clinical condition and hepatic biochemical tests. Subsequently, the frequency of monitoring may be lowered to once every 1 to 2 weeks, if the participant's clinical condition and laboratory results stabilize. Monitoring of ALT, AST, ALP, and TBL should continue until levels normalize or return to approximate baseline levels.

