- Participants should be referred to a mental health professional to assist in deciding whether the subject should be discontinued from study intervention. If a participant's psychiatric disorder can be adequately treated with psycho- and/or pharmacotherapy, then the subject, at the discretion of the investigator (in agreement with the mental health professional), may be continued in the trial on randomized therapy.
- o in addition, study intervention may be discontinued if participants:
 - answered "yes" to either Question 4 (Active Suicidal Ideation with Some Intent to Act, Without Specific Plan) on the "Suicidal Ideation" portion of the C-SSRS

or

 answered "yes" to Question 5 (Active Suicidal Ideation with Specific Plan and Intent) on the "Suicidal Ideation" portion of the C-SSRS

or

 answered "yes" to any of the suicide-related behaviors (Actual attempt, Interrupted attempt, Aborted attempt, Preparatory act or behavior) on the "Suicidal Behavior" portion of the C-SSRS.

Note: A psychiatrist or appropriately trained professional may assist in the decision to discontinue the participant.

• discontinuation due to a hepatic event or liver test abnormality

- o Participants who are discontinued from IP due to a hepatic event or liver test abnormality should have additional hepatic safety data collected via eCRF.
- Discontinuation of the IP for abnormal liver tests should be considered by the investigator when a participant meets 1 of the following conditions after consultation with the Lilly designated medical monitor:
 - ALT or aspartate aminotransferase (AST) >8× ULN
 - ALT>2× baseline value OR ≥300 U/L, whichever occurs first, if baseline ALT>2× ULN
 - ALT or AST >5× ULN for more than 2 weeks
 - ALT or AST >3× ULN and TBL >2× ULN or international normalized ratio (INR) >1.5
 - ALT or AST >3× ULN with the appearance of fatigue, nausea, vomiting, right upper-quadrant pain or tenderness, fever, rash, and/or eosinophilia (>5%)
 - ALP $>3 \times$ ULN
 - ALP >2.5× ULN and TBL >2× ULN
 - ALP >2.5× ULN with the appearance of fatigue, nausea, vomiting, right-quadrant pain or tenderness, fever, rash, and/or eosinophilia (>5%)

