8.2.4.1.2. Comprehensive Hepatic Evaluation

A comprehensive evaluation should be performed to search for possible causes of liver injury if one or more of these conditions occur:

If a participant with baseline results of	develops the following elevations:
ALT or AST <1.5× ULN	ALT or AST ≥3× ULN with hepatic signs/symptoms*, or
	ALT or AST ≥5× ULN
ALP <1.5× ULN	ALP ≥3× ULN
TBL <1.5× ULN	TBL ≥2× ULN (except for participants with Gilbert's syndrome)
ALT or AST ≥1.5× ULN	ALT or AST ≥2× baseline with hepatic signs/symptoms*, or
	ALT or AST ≥3× baseline
ALP≥1.5× ULN	ALP ≥2× baseline
TBL ≥1.5× ULN	TBL ≥1.5× baseline (except for participants with Gilbert's syndrome)

Abbreviations: ALP = alkaline phosphatase; ALT = alanine aminotransferase; AST = aspartate aminotransferase; TBL = total bilirubin; ULN = upper limit of normal.

At a minimum, this evaluation should include

- physical examination
- a thorough medical history, as outlined above
- tests for prothrombin time, INR (PT-INR)
- tests for viral hepatitis A, B, C, or E
- tests for autoimmune hepatitis, and
- an abdominal imaging study, for example, ultrasound or CT scan.

Based on the participant's history and initial results, further testing should be considered in consultation with the Lilly-designated medical monitor, including tests for

- hepatitis D virus
- cytomegalovirus
- Epstein-Barr virus
- acetaminophen levels
- acetaminophen protein adducts
- urine toxicology screen
- Wilson's disease
- blood alcohol levels
- urinary ethyl glucuronide, and
- serum phosphatidylethanol.

Based on the circumstances and the investigator's assessment of the participant's clinical condition, the investigator should consider referring the participant for

^{*} Hepatic signs/symptoms are severe fatigue, nausea, vomiting, right upper quadrant abdominal pain, fever, rash, and/or eosinophilia >5%.

- a hepatologist or gastroenterologist consultation
- magnetic resonance cholangiopancreatography
- endoscopic retrograde cholangiopancreatography
- cardiac echocardiogram, or
- a liver biopsy.

Additional hepatic data collection (hepatic safety CRF) in study participants who have abnormal liver tests during the study

Additional hepatic safety data collection in hepatic safety CRF should be performed in study participants who meet 1 or more of the following 5 conditions:

- 1. Elevation of serum ALT to \geq 5× ULN on 2 or more consecutive blood tests (if baseline ALT <1.5× ULN)

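### Section 8.2.4.1.1 sends repeat liver tests to the hypersensitivity appendix and does not ask for the INR that a Section 7.1 discontinuation condition uses

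*Protocol*

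**What the plan says.** Four places in the protocol bear on this.

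- **Section 8.2.4.1.1 (Close Hepatic Monitoring)** sets the first tier. With baseline ALT/AST below 1.5× ULN it starts at 3× ULN. With a baseline of 1.5× ULN or more it starts at "ALT or AST ≥2× baseline". The instruction for that point is "Laboratory tests (Appendix 3 [Section 10.3]), including ALT, AST, ALP, TBL, direct bilirubin, GGT, and creatine kinase, should be repeated", and the time allowed is 48 to 72 hours. Later monitoring covers ALT, AST, ALP and TBL.
- **Section 8.2.4.1.2 (Comprehensive Hepatic Evaluation)** sets the second tier and is the first place where PT-INR is a minimum test. With baseline ALT/AST below 1.5× ULN it starts at 5× ULN, or at 3× ULN with hepatic signs or symptoms. With a higher baseline it starts at 3× baseline, or at "ALT or AST ≥2× baseline with hepatic signs/symptoms". It also starts on TBL or ALP alone.
- **Section 7.1** states that "Discontinuation of the IP for abnormal liver tests should be considered by the investigator when a participant meets 1 of the following conditions". The sponsor's medical monitor is to be consulted as part of this. One of the eight conditions is "ALT or AST >3× ULN and TBL >2× ULN or international normalized ratio (INR) >1.5".
- **Appendices.** Appendix 3 (Section 10.3) covers hypersensitivity events: antidrug antibodies, drug concentration, tryptase, N-methylhistamine, IgE, basophil activation, complement and cytokines. Appendix 7 (Section 10.7) is the liver list. It includes PT-INR, but refers back to Section 8.2.4.1 for the choice of tests. Neither the Schedule of Activities nor the routine panel in Appendix 2 contains a coagulation test.

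**The concern.** A site that follows Section 8.2.4.1.1 to its cited appendix finds nothing about the liver. A site that follows the seven named tests has every laboratory value the Section 7.1 liver conditions need except INR and the eosinophil count. The eosinophil count counts only as one of several listed signs, whereas INR is half of a condition in its own right. In the band between the two tiers, the discontinuation condition can therefore go unassessed simply because nobody was told to draw the test. What is at stake is uniform assessment of one hepatic safety condition across sites, not an efficacy analysis.

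**Working it through.** There is no plan figure to reproduce. The check sets the thresholds of Sections 7.1, 8.2.4.1.1 and 8.2.4.1.2 side by side. All multiples are of ULN unless marked otherwise, and b is the baseline ALT/AST.

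**Is PT-INR in the first tier?** The named tests are ALT, AST, ALP, TBL, direct bilirubin, GGT and creatine kinase: PT-INR is 0 of 7. The word *including* leaves the list open, but the appendix it points to has no INR either.

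**Baseline below 1.5×.** The first tier starts at 3×. Without symptoms, and below the TBL and ALP triggers, the second tier starts at 5×. Section 7.1 uses above 3×. INR is therefore not required from above 3× to below 5×. Within that band, with TBL below 2×, ALP below 3× and no symptom on either the 7.1 or the 8.2.4.1.2 list, the eight Section 7.1 conditions are:

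| Section 7.1 condition | Can it be met here? |
|---|---|
| ALT/AST above 8× | No, below 5× |
| ALT above 2× baseline or at least 300 U/L, if baseline ALT is above 2× | No, baseline below 1.5× |
| ALT/AST above 5× for more than 2 weeks | No, below 5× |
| ALT/AST above 3× with TBL above 2× or INR above 1.5 | TBL arm no; **INR arm yes** |
| ALT/AST above 3× with symptoms | No symptoms |
| ALP above 3× | No, below 3× |
| ALP above 2.5× and TBL above 2× | No, TBL below 2× |
| ALP above 2.5× with symptoms | No symptoms |

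One of eight remains, and it depends on the value that is not required. The two symptom lists differ: Section 7.1 accepts any fatigue and adds tenderness, while Section 8.2.4.1.2 needs severe fatigue. A participant with non-severe fatigue already meets a 7.1 condition without INR, so the result is confined to participants with no symptom on either list.

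**Raised baseline.** Without symptoms, and below the TBL and ALP triggers, the second tier starts at 3b and the repeat rule at 2b.

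| b | INR not required | Part that can meet a 7.1 condition without INR | Still open if PT-INR is added to the repeat |
|---|---|---|---|
| 1.5× | above 3.0× to below 3 × 1.5 = 4.5× | none | none (2 × 1.5 = 3.0×) |
| 2.0× | above 3.0× to below 3 × 2.0 = 6.0× | above 5.0×, if it lasts more than 2 weeks | above 3.0× to below 4.0× |
| 3.0× (highest ALT eligible at screening) | above 3.0× to below 3 × 3.0 = 9.0× | ALT above 2 × 3.0 = 6.0×; also above 5.0× if it lasts more than 2 weeks | above 3.0× to below 6.0× |

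At b = 3.0×, the ALT rule relative to baseline alone covers (9.0 − 6.0)/(9.0 − 3.0) = half of the range. That rule applies to ALT only, and only when baseline ALT is above 2×. Its 300 U/L limb may apply sooner, but the laboratory's ULN is not given.

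**The case against.** The other side has a fair case. The sentence in Section 8.2.4.1.1 names the seven tests itself, so a site can act without opening any appendix. Because Appendix 7 hands test selection back to Section 8.2.4.1, correcting the reference alone would not make PT-INR required. A tiered scheme, in which the early repeat confirms the abnormality and its direction and a synthetic-function test follows later, is a legitimate design. Appendix 2 lets the investigator add tests. Section 8.2.4.1.1 brings in the medical monitor if the abnormality persists or worsens, with checks 1 to 3 times weekly at first. Section 7.1 asks only that discontinuation be considered.

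All of this limits the weight of the point. None of it supplies the INR value: discretion, an open-ended list and consultation do not require the test, and the reference is wrong in an operative safety rule.

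A reader might infer more from the raised-baseline ranges, for instance that at b = 3.0× a discontinuation decision depends on INR all the way from 3× to 9× ULN. The documents do not support that. INR is not required in that range, but ALT above 6× already meets a 7.1 condition there, and ALT/AST above 5× for more than 2 weeks is another route without INR. A reader might also infer that PT-INR should be drawn whenever ALT or AST exceeds 3× ULN, whatever the baseline. That would add an absolute trigger to a scheme built relative to baseline, in a population in which more than 40% are to have NAFLD. A participant moving from 2.9× to 3.1× would need the test. That is a debatable trade-off, not the correction of an error.

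**Conclusion.** The concern holds as a minor defect. The appendix reference is wrong, and no rule requires INR in a band where INR is the only available Section 7.1 liver condition. That band is baseline ALT/AST below 1.5× ULN, current ALT or AST above 3× and below 5× ULN, TBL below 2× ULN, ALP below 3× ULN, and no symptom on either list. With a raised baseline INR is likewise not required up to 3× baseline, but that whole range should not be presented as decision-relevant.

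This rests on reading the 7.1 condition as ALT/AST above 3× ULN together with either TBL above 2× ULN or INR above 1.5, and on baseline TBL and ALP below 1.5× ULN for the second-tier triggers. The number of participants who would fall in the band cannot be derived from the documents. Sample size, endpoints and efficacy analyses are unaffected. Nothing in the plan prevents an INR from being drawn, so it would be wrong to conclude that these participants go unmonitored.

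**What to change.** In Section 8.2.4.1.1, replace the reference to Appendix 3 (Section 10.3) with Appendix 7 (Section 10.7), and add PT-INR to the tests done at the 48 to 72 hour repeat. Both parts are needed, because Appendix 7 does not itself require any test. This closes the gap for baselines up to 1.5× ULN and alters no threshold or discontinuation condition.

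The cost is amendment wording and one coagulation tube at a draw already triggered. PT-INR would also be drawn at repeats triggered by ALP or TBL alone. Routine clinical chemistry during treatment falls only at Weeks 24, 52 and 72.

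Whether to test participants with a raised baseline who are above 3× ULN but below 2× baseline is left to the sponsor.

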8.2.4.1.2. Comprehensive Hepatic Evaluation

A comprehensive evaluation should be performed to search for possible causes of liver injury if one or more of these conditions occur:

If a participant with baseline results of	develops the following elevations:
ALT or AST <1.5× ULN	ALT or AST ≥3× ULN with hepatic signs/symptoms*, or
	ALT or AST ≥5× ULN
ALP <1.5× ULN	ALP ≥3× ULN
TBL <1.5× ULN	TBL ≥2× ULN (except for participants with Gilbert's syndrome)
ALT or AST ≥1.5× ULN	ALT or AST ≥2× baseline with hepatic signs/symptoms*, or
	ALT or AST ≥3× baseline
ALP≥1.5× ULN	ALP ≥2× baseline
TBL ≥1.5× ULN	TBL ≥1.5× baseline (except for participants with Gilbert's syndrome)

Abbreviations: ALP = alkaline phosphatase; ALT = alanine aminotransferase; AST = aspartate aminotransferase; TBL = total bilirubin; ULN = upper limit of normal.

At a minimum, this evaluation should include

- physical examination
- a thorough medical history, as outlined above
- tests for prothrombin time, INR (PT-INR)
- tests for viral hepatitis A, B, C, or E
- tests for autoimmune hepatitis, and
- an abdominal imaging study, for example, ultrasound or CT scan.

Based on the participant's history and initial results, further testing should be considered in consultation with the Lilly-designated medical monitor, including tests for

- hepatitis D virus
- cytomegalovirus
- Epstein-Barr virus
- acetaminophen levels
- acetaminophen protein adducts
- urine toxicology screen
- Wilson's disease
- blood alcohol levels
- urinary ethyl glucuronide, and
- serum phosphatidylethanol.

Based on the circumstances and the investigator's assessment of the participant's clinical condition, the investigator should consider referring the participant for

^{*} Hepatic signs/symptoms are severe fatigue, nausea, vomiting, right upper quadrant abdominal pain, fever, rash, and/or eosinophilia >5%.

- a hepatologist or gastroenterologist consultation
- magnetic resonance cholangiopancreatography
- endoscopic retrograde cholangiopancreatography
- cardiac echocardiogram, or
- a liver biopsy.

Additional hepatic data collection (hepatic safety CRF) in study participants who have abnormal liver tests during the study

Additional hepatic safety data collection in hepatic safety CRF should be performed in study participants who meet 1 or more of the following 5 conditions:

- 1. Elevation of serum ALT to \geq 5× ULN on 2 or more consecutive blood tests (if baseline ALT <1.5× ULN)
 - ➤ In participants with baseline ALT \ge 1.5× ULN, the threshold is ALT \ge 3× baseline on 2 or more consecutive tests
- 2. Elevated TBL to ≥2× ULN (if baseline TBL <1.5× ULN) (except for cases of known Gilbert's syndrome)
 - ➤ In participants with baseline TBL $\ge 1.5 \times$ ULN, the threshold should be TBL $\ge 2 \times$ baseline
- 3. Elevation of serum ALP to $\ge 2 \times$ ULN on 2 or more consecutive blood tests (if baseline ALP <1.5× ULN)
 - ➤ In participants with baseline ALP $\ge 1.5 \times$ ULN, the threshold is ALP $\ge 2 \times$ baseline on 2 or more consecutive blood tests
- 4. Hepatic event considered to be an SAE
- 5. Discontinuation of study drug due to a hepatic event

Note: the interval between the 2 consecutive blood tests should be at least 2 days.

8.2.5. Depression, Suicidal Ideation and Behavior Risk Monitoring

Overweight and obese patients are at increased risk for depression (Luppino et al. 2010). Depression can increase the risk for suicidal ideation and behavior. Therefore, study participants will be screened at trial entry and monitored during the study for depression, and suicidal ideation and behavior.

Participants should be monitored appropriately and observed closely for suicidal ideation and behavior or any other unusual changes in behavior, especially at the beginning and end of the course of treatment, or at the time of dose changes, either increases or decreases. Consideration should be given to discontinuing study medication in subjects who experience signs of suicidal ideation or behavior, following a risk assessment (Section 10.4.7.12).

Baseline and treatment-emergent assessment of depression, suicidal ideation and behavior will be monitored during the study using the C-SSRS and PHQ-9 (Section 10.4.7.12).

8.2.6. Special Safety Topics

Adverse events of special interest (AESIs) are AEs which the sponsor specifies as being of special interest based on standard drug registration topics, safety findings from previous studies in development program, potential risks associated with GLP-1 receptor agonists as noted in product labels and published literature, and comorbidities and risk factors prevalent in the studied populations.

AESIs for this program include:

- a) severe hypoglycemia
- b) pancreatitis (adjudicated)
- c) thyroid malignancies and C-cell hyperplasias
- d) major adverse cardiovascular events (adjudicated); includes, but not limited to cardiovascular death, nonfatal myocardial infarction, nonfatal stroke, and hospitalization for heart failure
- e) supraventricular arrhythmias and cardiac conduction disorders
- f) hypersensitivity events
- g) injection site reactions
- h) allergic/hypersensitivity reactions; includes injection site reactions and antidrug antibody (ADA) formation
- i) hepatobiliary disorders
- i) severe GI AEs
- k) acute renal events
- 1) depression, suicidal ideation, or behavior

If "a" to "l" above are reported, sites will be prompted to collect additional details/data.

Please see Appendix 4 (Section 10.4), for detailed information.

8.3. Adverse Events, Serious Adverse Events, and Product Complaints

The definitions of the following events can be found in Appendix 4 (Section 10.4).

- AEs
- SAEs
- product complaints (PCs)

These events will be reported by the participant (or, when appropriate, by a caregiver, surrogate, or the participant's legally authorized representative).

The investigator and any qualified designees are responsible for detecting, documenting, and recording events that meet these definitions and remain responsible for following up events that are serious, considered related to the study intervention, study device or device constituent, or study procedures, or that caused the participant to discontinue the study intervention (see Section 7).

The investigator remains responsible for following, through an appropriate health care option, AEs that are serious or otherwise medically important, considered related to the study intervention or the study, or that caused the participant to discontinue the study intervention before completing the study. The participant should be followed until the event resolves, stabilizes with appropriate diagnostic evaluation, or is reasonably explained. The frequency of follow-up evaluations of the AE is left to the discretion of the investigator.

Lack of drug effect is not an AE in clinical studies, because the purpose of the clinical study is to establish treatment effect.

After the ICF is signed, study site personnel will record via eCRF the occurrence and nature of each participant's preexisting conditions, including clinically significant signs and symptoms of the disease under treatment in the study. In addition, site personnel will record any change in the condition(s) and any new conditions as AEs. Investigators should record their assessment of the potential relatedness of each AE to protocol procedure and study intervention via eCRF.

The investigator will interpret and document whether or not an AE has a reasonable possibility of being related to study treatment, study device, or a study procedure, taking into account the disease, concomitant treatment, or pathologies.

A "reasonable possibility" means that there is a cause and effect relationship between the IP, study device, and/or study procedure and the AE.

The investigator answers yes/no when making this assessment.

Planned surgeries and nonsurgical interventions should not be reported as AEs unless the underlying medical condition has worsened during the course of the study.

If a participant's study intervention is discontinued as a result of an AE, study site personnel must report this to Lilly or its designee via eCRF, clarifying if possible, the circumstances leading to any dosage modifications or discontinuations of treatment.

Care will be taken not to introduce bias when detecting events. Open-ended and non-leading verbal questioning of the participant is the preferred method to inquire about event occurrences.

After the initial report, the investigator is required to proactively follow each participant at subsequent visits/contacts. All SAEs, and AEs of special interest (as defined in Section 9.4.4.3), will be followed until resolution, stabilization, the event is otherwise explained, or the participant is lost to follow-up (as defined in Section 7.3). For product complaints, the investigator is responsible for ensuring that follow-up includes any supplemental investigations as indicated to elucidate the nature and/or causality. Further information on follow-up procedures is provided in Appendix 10 (Section 10.10).

